### 3.3 Primary endpoints

The primary endpoints for the three primary objectives are:

1. Composite MACE at 30 days post vaccination (preferred by cardiovascular community) and at 42 days post vaccination (preferred by vaccine monitoring investigators) including any of:
  - Death from any cause.
  - Ventricular arrhythmia (ventricular fibrillation or ventricular tachycardia).
  - Heart block (type II or type III block).
  - Heart failure (national guideline criteria).
  - Left ventricular systolic dysfunction (left ventricular ejection fraction [LVEF] <55%).
  - Cardiac tamponade.
2. Recovery of cardiac function in patients with previously documented abnormal cardiac function (LVEF<55% during anytime at baseline), with LVEF increase by 5% from worst baseline measurement.
3. Quality of life, depression, anxiety, and physical activity using validated instruments at baseline, 3 months, 12 months, and annually.
  - 3a. Quality of life: EQ-5D-5L questionnaire for adults or EQ-5D-Y questionnaire for children.
  - 3b. Depression and anxiety data: PHQ-9 and GAD-7.
  - 3c. Physical activity: International Activity Questionnaire.

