## 4.5 Inclusion criteria

### 4.5.1 Inclusion criteria for vaccine associated myocarditis/pericarditis.

1. COVID-19 vaccination within previous 42 days.

AND

2. At least one cardiac symptom of suspected myocarditis/pericarditis (Appendix 5).

OR

At least two non-specific symptoms (Appendix 5).

OR

In infants and young children, at least two non-specific pediatric symptoms (Appendix 5).

OR

No symptoms, but abnormal histopathology or a combination of abnormal cardiac biomarkers with abnormal cardiac imaging (echo or MRI).

AND

3. At least one of the following objective findings (Brighton Criteria case definitions, Appendices 1 to 5):
  - a. Histopathologic examination of myocardial tissue (autopsy or endomyocardial biopsy) showed myocardial inflammation.
  - b. Elevated myocardial biomarker (Troponin T, Troponin I, or CK-MB).
  - c. Cardiac MRI abnormality.
  - d. Echocardiographic abnormality.
  - e. New or worsening arrhythmia on electrocardiogram, Holter monitor, or telemetry.
  - f. Elevated inflammation biomarkers: ESR, CRP, hs-CRP, or D-Dimer.
  - g. Physical examination pericardial friction rub or pulsus paradoxus.
  - h. Pericardial fluid or inflammation by imaging (echo, MRI, or CT).
  - i. Enlarged heart on chest radiograph.

AND

4. No alternative cause of presentation. e.g. infectious or autoimmune myocarditis.

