## 7. APPENDICES

## 7.1 Appendix 1. Brighton Collaboration myocarditis case definition and levels of diagnostic certainty

Level of certainty 1 (definitive case)	
Histopathologic examination of myocardial tissue (autopsy or endomyocardial biopsy) showed myocardial inflammation	
OR	
Elevated myocardial biomarkers (at least one of the findings below)	
	Troponin T
	Troponin I
AND	
Abnormal imaging study	
	Abnormal cardiac magnetic resonance study (at least one of the findings below)
	Edema on T2-weighted study, typically patchy in nature
	Late gadolinium enhancement on T1-weighted study with an increased enhancement ratio between myocardial and skeletal muscle typically involving at least one non-ischemic regional distribution with recovery (myocyte injury).
OR	
	Abnormal echocardiogram (at least one of the findings below)
	New focal or diffuse left or right ventricular function abnormalities (e.g., decreased ejection fraction)
	Segmental wall motion abnormalities
	Global systolic or diastolic function depression or abnormality
	Ventricular dilation
	Wall thickness change
Level of certainty 2 (probable case)	
Clinical symptoms	
	Cardiac symptoms (at least one finding below)
	Acute chest pain or pressure
	Palpitations
	Dyspnea after exercise, at rest, or lying down
	Diaphoresis
	Sudden death
OR	
	Non-specific symptoms (at least two findings below)
	Fatigue
	Abdominal pain
	Dizziness or syncope
	Edema
	Cough
OR	
	Infants and young children (at least two findings below)
	Irritability
	Vomiting
	Poor feeding
	Tachypnea
	Lethargy
AND	
Testing supporting diagnosis (biomarkers, echocardiogram, and electrocardiogram)	
	Abnormal cardiac magnetic resonance study (see level 1 case definition)
OR	
	Elevated myocardial biomarkers (at least one of the findings below)
	Troponin T
	Troponin I
	Creatine kinase-myocardial band
OR	
	Abnormal echocardiogram (See level 1 case definition)
OR	
	Electrocardiogram abnormalities that are new and/or normalize on recovery (at least 1 of the findings below)
	Paroxysmal or sustained atrial or ventricular arrhythmias (premature atrial or ventricular beats, and/or supraventricular or ventricular tachycardia, interventricular conduction delay, abnormal Q waves, low voltages)
	AV nodal conduction delays or intraventricular conduction defects (atrioventricular block (grade I-III), new bundle branch block)
	Continuous ambulatory electrocardiographic monitoring that detects frequent atrial or ventricular ectopy
AND	

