**7.7 Appendix 7. Data collection variables**

Eligibility	Study inclusion/exclusion criteria Brighton Collaboration case definition criteria
Diagnosis	Myocarditis etiology Brighton Collaboration case definition level
Demographics	Age, date of birth (Month/year), gender, ethnicity Occupation, education, urban/rural Province, city, postal code (3 digit)
Vaccine	Doses 1, 2, 3, 4, 5, additional doses Vaccine type and date
Covid-19 infection	Infections 1, 2, 3, 4, 5, additional infections Date symptom onset Date diagnosis Diagnostic test (PCR, rapid antigen, self-report, other) Symptoms Treatment
Medical history	Cardiovascular risk factors and disease Autoimmune condition Non-cardiovascular disease
Medications	NSAID, colchicine, steroid, PPI, other
Laboratory tests	CBC, renal function Cardiac biomarkers, inflammatory markers
Examination	Vital signs and clinical signs if recorded
Hospitalization	Date admission and discharge Diagnosis Presentation Management
Death	Date Location Cause
Echocardiography	Left and right ventricular function Pericardial
Cardiac MRI	Left and right ventricular function Late gadolinium enhancement
ECG and Holter	Date ECG abnormalities Holter abnormalities Arrhythmia classification
Outcomes	Primary and secondary endpoints

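### Section 3.3 does not separate low LVEF, heart failure or heart block that predates the exposure from that which follows it, so known prior disease can count as MACE, and prior low LVEF can enter the recovery denominator

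*Protocol*

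**What the plan says.** Objective 1 (Protocol 3.1) is to evaluate the incidence of MACE. Section 3.3 item 1 sets the timing as "Composite MACE at 30 days post vaccination (preferred by cardiovascular community) and at 42 days post vaccination". Three of the six components describe a condition that a patient may already have:

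- "Left ventricular systolic dysfunction (left ventricular ejection fraction [LVEF] <55"%)
- "Heart failure (national guideline criteria")
- "Heart block (type II or type III block")

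None refers to onset, worsening or an earlier value.

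Item 2 is "Recovery of cardiac function in patients with previously documented abnormal cardiac function (LVEF<55% during anytime at baseline"), with success defined as a 5% rise from the worst baseline value. Under section 5 the baseline date is the vaccination date, but baseline data come from the first presentation, which is after it.

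Elsewhere the Protocol does use a condition of newness. Section 4.5.1 item 3e reads "New or worsening arrhythmia on electrocardiogram, Holter monitor, or telemetry", and Appendix 1 lists "New focal or diffuse left or right ventricular function abnormalities (e.g., decreased ejection fraction"). Appendix 7 collects "Cardiovascular risk factors and disease" as medical history; it does not list a pre-exposure LVEF or conduction status.

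**The concern.** A cohort drawn from all ages, with no exclusion for earlier heart disease, will contain some patients with known cardiomyopathy, heart failure or conduction disease. If the endpoint is applied literally, these patients are MACE cases whatever the index illness did to them. Three uses of the endpoint are affected:

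- **The headline rate** (objective 1) mixes prevalent with incident disease, in a study commissioned to inform vaccine decisions.
- **The treated/untreated comparison** in the vaccine cohort (3.2). If prior heart disease influences the choice of NSAID or colchicine, it affects both sides of the comparison.
- **The MACE risk score** (3.2). Prior heart disease would predict an outcome that is partly the same disease.

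The recovery endpoint has a narrower version of the problem. A chronically low LVEF enters the denominator with little prospect of meeting the success rule. The point concerns disease that predates the exposure, not findings of the index illness at presentation.

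**Working it through.** **1. Does any other section close the gap?**

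- Section 4.5.1 item 4, and its counterparts in 4.5.2 and 4.5.3, require that nothing else explains the acute presentation. That does not remove a patient with unrelated chronic disease.
- Section 4.6 excludes on consent, Brighton levels 4 and 5, and alternative diagnoses. It does not name prior cardiomyopathy, heart failure or conduction disease.
- The pericarditis definition (Appendix 3) does not use LVEF. A patient with a long-standing LVEF of 45% can therefore qualify through pericarditis, meet the LVEF component of item 1 and enter the item 2 denominator.
- In Appendix 1 the word new attaches to one of the five echocardiographic findings, so even the case definition gives only partial protection.

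**2. Effect on MACE.** The Protocol states no expected MACE rate, so there is no figure to reproduce. Its sample size (6.2) uses no event rate and does not change. Its lower limit, 0.60 × 810 = 486 cases, serves here only as a denominator.

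Let p be the true risk of a new event and q the prevalence of prior qualifying disease. Both are assumptions.

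Observed MACE = q + (1 − q)p

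| q | p = 5% | p = 10% | p = 20% |
|---|---|---|---|
| 1% | 5.95% | 10.9% | 20.8% |
| 3% | 7.85% | 12.7% | 22.4% |
| 5% | 9.75% | 14.5% | 24.0% |
| 10% | 14.5% | 19.0% | 28.0% |

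At p = 10% and 486 cases there are 48.6 true events. The excess is 486 × (1 − p) × q: 486 × 0.90 × 0.01 = 4.4 events at q = 1%, and 486 × 0.90 × 0.10 = 43.7 at q = 10%.

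**3. Effect on recovery.** Only LVEF matters here. Let s be the share of patients with a stably low prior LVEF (none of whom gain 5%), d the share of the rest with a new LVEF below 55%, and r the true recovery rate among those. All three are assumptions.

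Observed recovery = r(1 − s)d / [(1 − s)d + s]

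With d = 10% and r = 90%:

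- s = 1%: 0.0891 / 0.109 = 81.7%
- s = 3%: 0.0873 / 0.127 = 68.7%
- s = 5%: 0.0855 / 0.145 = 59.0%

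With d = 20% the figures are 85.7%, 77.9% and 71.3%.

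The bias depends on the low LVEF being stable. A patient who falls from 50% to 40% and returns to 50% counts as recovered under item 2.

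**The case against.** **The wording already implies new events.** Objective 1 speaks of incidence and item 1 is timed after vaccination, so a lifelong LVEF of 45% fits poorly as an event. Section 6.3 promises a statistical analysis plan, which could add a rule. It is also fair that no sentence orders prevalent disease to be counted. But the Protocol itself fixes the endpoint definition and leaves the condition out, although it states it for eligibility. A later plan also cannot use pre-exposure values that were never abstracted.

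**Prior disease can be separated at analysis.** Partly true: medical history would identify many known cases. It would not show whether LVEF or conduction had worsened.

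**A reader might infer a false difference between etiologies.** With 10% true risk in both cohorts and q of 1% against 5% to 10%, the rates would be 10.9% against 14.5% to 19.0%. The documents do not support this as a finding. No formal comparison of MACE or recovery between etiologies is planned, no passage gives the cardiac history of the COVID-19 cases, and the vaccine cohort also takes adults without a comorbidity limit. What remains is a risk when rates are read side by side.

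**A reader might also infer that prior heart failure or heart block counts as non-recovery.** It does not. Item 2 is defined by LVEF alone, so prior heart block and prior heart failure with preserved LVEF affect MACE only. Death and tamponade are acute events and are little affected.

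**The remedy misclassifies too.** Whether a finding is called new would depend on who had an earlier echocardiogram or ECG. This stands, and is why a sensitivity analysis belongs in the fix.

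**Conclusion.** The point holds as a defect of definition in two primary endpoints. As written, item 1 lets known prior low LVEF, heart failure or heart block count as incident MACE, and the bias is upward whatever the assumptions. Its size cannot be derived from the documents: at an assumed true risk of 10% it runs from 0.9 points (q = 1%) to 9.0 points (q = 10%), and it may be small among young vaccine cases. Item 2 is affected only through LVEF that was already below 55% and stays low; the recovery figures above illustrate this and assume that no such patient gains 5%. The sample size is untouched. This is a should-fix matter: the gap is real and cheap to close, but medical history is collected and no test between etiologies depends on it.

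**What to change.** - **Section 3.3 item 1:** count LVEF <55%, heart failure and heart block only if new, or documented as worse than the last record before the index exposure. Define the index date for COVID-19 and MIS-C/A cases as well, since item 1 is anchored only to vaccination. MIS-C/A needs particular care, because Appendix 6 allows qualification through close contact.
- **Patients with no earlier record:** treat them as new, report their number, and add a sensitivity analysis restricted to patients with no known prior cardiac disease.
- **Section 3.3 item 2:** take the primary recovery figure from patients without a documented LVEF <55% before exposure, and report those with one separately. Acute-on-chronic injury then stays visible.
- **Appendix 7:** add the last pre-exposure LVEF and conduction status, where charted.

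The cost is endpoint wording, two fields taken from charts already under review, and a MACE rate that is lower, only slightly so if prior disease is rare. Some misclassification remains where no earlier record exists. Eligibility, visits, tests and sample size do not change. Chart review is ongoing, so a later change would mean going back to charts already abstracted.

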### 3.4 Secondary endpoints

- Individual components of primary composite endpoint at 30 days and 42 days post vaccination.
- Atrial arrhythmias.
- All-cause and cardiovascular mortality.
- All-cause and cardiovascular hospitalization.
- Recurrence of myocarditis/pericarditis.
- Constrictive pericarditis.

## 4. STUDY DESIGN

### 4.1 Study design

The surveillance study is a cohort study combining 1) passive surveillance by chart review, 2) active surveillance by prospective follow-up integrated with standard clinical care.

## 4.2 Study setting

The study is a multi-centre study conducted in secondary and tertiary care centres treating myocarditis and pericarditis in the inpatient or outpatient setting in all provinces and territories in Canada.

## 4.3 Study population

The study population will include any patient with:

1. Vaccine associated myocarditis/pericarditis.
2. COVID-19 myocarditis/pericarditis.
3. MIS-C/A myocarditis/pericarditis
4. Alternative etiology myocarditis.

Patients will be required to satisfy the inclusion and exclusion criteria. Eligibility waivers to the inclusion/exclusion criteria are not permitted.

## 4.4 Definitions

Patients will be diagnosed based on the Brighton Collaboration case definitions of the term “myocarditis” and “pericarditis”. This utilizes five degrees of certainty, of which three will be included: definitive case (level 1), probable case (level 2), and possible case (level 3). The Level 1 definition is highly specific for the identification of a case of myocarditis and pericarditis. Levels 2 and 3 offer a stepwise increase of sensitivity, with acceptable specificity. In this way it is hoped that all possible cases of myocarditis and pericarditis can be captured. Two additional levels (Levels 4 and 5) are helpful for real-world analysis. Level 4 cases are reported myocarditis or pericarditis with insufficient evidence to meet the case definition of vaccine-induced cardiac inflammation. These are anticipated from centres without easy access to cardiac investigations. Level 5 cases are defined as “Not a case of myocarditis or pericarditis”. These are anticipated to be cases of undifferentiated chest-pain without objective findings of myocarditis or pericarditis.

## 4.5 Inclusion criteria

### 4.5.1 Inclusion criteria for vaccine associated myocarditis/pericarditis.

1. COVID-19 vaccination within previous 42 days.

AND

2. At least one cardiac symptom of suspected myocarditis/pericarditis (Appendix 5).

OR

At least two non-specific symptoms (Appendix 5).

OR

In infants and young children, at least two non-specific pediatric symptoms (Appendix 5).

OR

No symptoms, but abnormal histopathology or a combination of abnormal cardiac biomarkers with abnormal cardiac imaging (echo or MRI).

AND

3. At least one of the following objective findings (Brighton Criteria case definitions, Appendices 1 to 5):
  - a. Histopathologic examination of myocardial tissue (autopsy or endomyocardial biopsy) showed myocardial inflammation.
  - b. Elevated myocardial biomarker (Troponin T, Troponin I, or CK-MB).
  - c. Cardiac MRI abnormality.
  - d. Echocardiographic abnormality.
  - e. New or worsening arrhythmia on electrocardiogram, Holter monitor, or telemetry.
  - f. Elevated inflammation biomarkers: ESR, CRP, hs-CRP, or D-Dimer.
  - g. Physical examination pericardial friction rub or pulsus paradoxus.
  - h. Pericardial fluid or inflammation by imaging (echo, MRI, or CT).
  - i. Enlarged heart on chest radiograph.

AND

4. No alternative cause of presentation. e.g. infectious or autoimmune myocarditis.

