## 2.4 Case definition of vaccine associated myocarditis/pericarditis

There are two major case definition criteria currently in use for post-vaccine myocarditis. These are from the CDC and the Brighton Collaboration. They are very similar, but the Brighton Collaboration criteria have been updated and more widely used (Appendices 1 to 5). Similarities include some symptom combinations, troponin positivity, histopathologic confirmation, cardiac magnetic resonance imaging features of myocarditis and echocardiographic abnormalities. For the purposes of our study, we will primarily use Brighton Criteria case definitions for myocarditis and pericarditis because they are more inclusive. However, the CDC criteria will also be analysed to allow for international comparison.

This study will also include patients with COVID-19 myocarditis/pericarditis and MIS-C/A myocarditis. COVID-19 myocarditis/pericarditis will use the same case definitions as vaccine-myocarditis/pericarditis, but the precipitant is COVID-19 infection in the prior 42 days. MIS-C/A myocarditis uses the same case definition as Brighton criteria for vaccine myocarditis, but requires the criteria for MIS-C/A to be met (see Appendix 6).

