**7.3 Appendix 3. Brighton Collaboration pericarditis case definition and levels of diagnostic certainty**

Level of certainty 1 (definitive case)	
	Histopathologic examination of myocardial tissue (autopsy or pericardial biopsy) showed pericardial inflammation OR Abnormal testing (at least two of the following three findings below): Evidence of abnormal fluid collection or pericardial inflammation by imaging (echocardiogram, magnetic resonance, cardiac magnetic resonance, computed tomography) OR Electrocardiogram abnormalities that are new or normalize on recovery (must have all findings below) Diffuse concave-upward ST-segment elevation ST-segment depression in augmented vector right PR-depression throughout the leads without reciprocal ST-segment changes OR Physical examination finding (at least one finding below) Pericardial friction rub Distant heart sounds (infants and children) Pulsus paradoxus
Level of certainty 2 (probable case)	
Clinical symptoms	Cardiac symptoms (at least one finding below) Acute chest pain or pressure Palpitations Dyspnea after exercise, at rest, or lying down Diaphoresis Sudden death OR Infants and young children (at least two findings below) Irritability Vomiting Poor feeding Tachypnea Lethargy AND Physical examination findings: (at least one finding below) Pericardial friction rub Pulsus paradoxus OR Evidence of abnormal fluid collection or pericardial inflammation by imaging (echocardiogram, magnetic resonance, cardiac magnetic resonance, computed tomography) OR Electrocardiogram abnormalities that are new and/or normalize on recovery (at least 1 finding below) Diffuse concave-upward ST-segment elevation ST-segment depression in augmented vector right PR-depression throughout the leads without reciprocal ST-segment changes AND No alternative diagnosis for symptoms (myocardial infarction, pulmonary embolus, mediastinitis etc.)
Level of certainty 3 (possible case)	

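### Protocol 4.5.1 items 2 and 3, read literally, refuse some Brighton level 1–3 vaccine cases that 4.4 says are included

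*Protocol*

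**What the plan says.** Section 4.4 diagnoses patients by the Brighton definitions and says that of five levels "three will be included: definitive case (level 1), probable case (level 2), and possible case (level 3" are taken. It gives the aim: "In this way it is hoped that all possible cases of myocarditis and pericarditis can be captured". Section 2.4 gives the reason for the choice: "we will primarily use Brighton Criteria case definitions for myocarditis and pericarditis because they are more inclusive". Section 4.3 rules out eligibility waivers.

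Section 4.5.1 then lists four numbered criteria for vaccine cases, joined by AND. Two matter here.

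- **Item 2** asks for symptoms, or, failing that: "No symptoms, but abnormal histopathology or a combination of abnormal cardiac biomarkers with abnormal cardiac imaging (echo or MRI".
- **Item 3** asks for "At least one of the following objective findings (Brighton Criteria case definitions, Appendices 1 to 5" and lists entries a to i. The only explicitly electrocardiographic entry is 3e: "New or worsening arrhythmia on electrocardiogram, Holter monitor, or telemetry". The histology entry (3a) concerns myocardial inflammation. The examination entry (3g) names a rub or pulsus paradoxus.

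Appendix 3 is wider. Level 1 pericarditis is met by histology ("autopsy or pericardial biopsy) showed pericardial inflammation") or by "Abnormal testing (at least two of the following three findings below", the three being imaging, ECG and examination. No symptom is required at that level. Level 2 accepts symptoms plus a single pericarditis ECG change, and level 3 accepts nonspecific ECG change with its own symptom set. Appendix 1 accepts ST/T change for level 3 myocarditis.

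**The concern.** Two sections define the same population differently, and neither is said to prevail. A site that screens on the numbered criteria of 4.5.1, with no waiver available, will refuse patients whom 4.4 places in the study. Section 4.6 does not repair this. It removes levels 4 and 5 and alternative diagnoses, but it brings back nobody refused under 4.5.1.

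At stake is who forms the vaccine cohort, and therefore the denominator for the MACE, recovery and functional results in that group. Section 6.2 also sets the goal of identifying all 1,061 cases reported to the public health agency. Those are counted by Brighton levels 1 to 3, not by list a to i, so the target and the entry rule do not describe the same set.

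**Working it through.** The plan states no figure on this point, so there is none to reproduce. The check sets the two texts side by side. Items 1 and 4 of 4.5.1 (vaccination within 42 days, no alternative cause) are taken as met. Entry 3e is read as broadly as Appendix 1 allows, so conduction defects, abnormal Q waves and low voltage count as covered, because Appendix 1 level 2 lists Q waves and low voltage within its arrhythmia entry.

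**Item 3: Brighton findings against list a to i**

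| Finding | Accepted by | Entry in a to i |
|---|---|---|
| ST/T change | Appendix 1, level 3 | none |
| Reduced R-wave height | Appendix 1, level 3 | none |
| Diffuse ST elevation, ST depression in aVR, PR depression | Appendix 3, level 2 (any one) and level 1 (all three, with imaging or an examination sign) | none |
| Nonspecific non-arrhythmic ECG change | Appendix 3, level 3 | none |
| Pericardial inflammation on histology | Appendix 3, level 1 | none (3a is myocardial) |
| Distant heart sounds | Appendix 3, level 1 | none (3g omits it) |
| Raised troponin, CK-MB, CRP, ESR or D-dimer | Appendix 1, levels 1 to 3 | 3b, 3f |
| Abnormal echo or MRI, pericardial fluid, rub, enlarged heart | Appendices 1 and 3 | 3c, 3d, 3g, 3h, 3i |

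**Worked cases**

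1. Chest pain and diffuse ST elevation, nothing else. Appendix 3: cardiac symptom plus one listed ECG change, so level 2 pericarditis. In 4.5.1, item 2 is met and no entry of item 3 is met. Refused.
2. Chest pain and new T-wave inversion, nothing else. Appendix 1: level 3 myocarditis. Item 3 is not met. Refused.
3. No symptoms, effusion on echo, full pericarditis ECG, normal cardiac biomarkers. Appendix 3: two of three tests, so level 1 pericarditis. Item 3 is met by 3h. Item 2 is not met, because there is neither histopathology nor a raised cardiac biomarker. Refused.
4. Pericardial inflammation on biopsy, nothing else listed. Appendix 3: level 1 pericarditis. Item 2 is met, with or without symptoms. Item 3 is not met. Refused.

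**What is not refused.** Level 1 myocarditis passes both items even without symptoms, since histology or troponin plus echo/MRI is what item 2 asks for. Level 2 myocarditis passes on the broad reading of 3e. Level 3 myocarditis by inflammatory markers passes through 3f.

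Enumerating five symptom states with up to three of 16 findings, with conduction defects counted under 3e, gives the same kinds of refused case and no refused level 1 or level 2 myocarditis.

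**The other groups.** Sections 4.5.2 and 4.5.3 require myocarditis or pericarditis by the Brighton criteria for vaccine cases. If that means the appendices, case 1 enters the COVID-19 group but not the vaccine group. If it points back to 4.5.1, case 1 is refused in every group. Either reading leaves a conflict with 4.4.

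**The case against.** **Intent is clear.** The stem of item 3 cites the appendices, 5.2 extracts chart information for the Brighton criteria, and Appendix 7 records the Brighton criteria and level. List a to i looks like an incomplete summary. This stands as evidence of intent, but a closed list with no waivers does not import findings it leaves out.

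**Few patients may be touched.** Section 5.1.1 lists routine blood work, ECG, Holter, echo and MRI at baseline, so many symptomatic patients will have another listed finding. This also stands and bounds the point. It is not complete protection: 4.10 extracts only what was already in the chart, so a test never done cannot rescue a case.

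**Three stronger readings are not supported.**

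- A reader might infer a biased MACE comparison between the vaccine and COVID-19 groups. That depends on one reading of 4.5.2 and 4.5.3. Section 2.4 says COVID-19 cases use the same definitions as vaccine cases, and item 3 labels its own list as Brighton, so the back-reference to 4.5.1 is at least as natural. Objective 1 describes MACE and states no comparison between etiologies. The only MACE comparison, in 3.2, is by treatment within vaccine cases.
- A reader might infer that vaccine-group MACE would be inflated, since patients refused by item 3 have no listed echo, MRI or arrhythmia finding. The protocol gives neither their number nor their event rate, so no effect on MACE can be shown.
- A reader might count refused routes and offer a fraction as the size of the problem. Such fractions change with how the signs are split and say nothing about patients.

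**Conclusion.** The contradiction is real as written: 4.5.1 refuses vaccine cases that 4.4 and Appendices 1 and 3 include. The cases are chiefly symptomatic ECG-only pericarditis (level 2 or 3), level 3 myocarditis by ST/T change, and symptom-free level 1 pericarditis. Pericardial histology and distant heart sounds are further gaps. The number of patients cannot be derived from the protocol. It is limited to those with nothing else that satisfies the item they fail.

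This rests on reading list a to i as closed and 3e broadly. The pericarditis flow chart in Appendix 4 is not visible in the text at hand, so the check uses the Appendix 3 table.

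Section 4.5.4 is only a wording matter. It has no criterion separating its group from the other three, and its no-alternative-cause clause sits badly with the heading if read with the example in 4.5.1 (infectious or autoimmune myocarditis), but fits if read with the example in 4.6 (myocardial infarction). That group has baseline data only and is in no stated objective, so a larger consequence should not be inferred.

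**What to change.** Reconcile 4.5.1 items 2 and 3 with 4.4 and Appendices 1 and 3. The simplest way is to replace both with one criterion: meets Brighton level 1, 2 or 3 for myocarditis or pericarditis (Appendices 1 and 3). The alternative is to complete both items so that they match the appendices. Use the same explicit reference in 4.5.2 to 4.5.4, so that all groups are judged by one definition whichever way the present wording was meant. Re-check any charts screened out on item 2 or item 3.

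In 4.5.4, as a clarification, state that the patient does not meet 4.5.1, 4.5.2 or 4.5.3, and say which alternative causes the clause means.

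The cost is a few protocol lines, ethics approval of the amendment (4.13.6), the matching eligibility fields, and the chart re-check. No tests are added, and Appendix 7 already collects the Brighton criteria and level.
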